11 STATISTICAL METHODS

Descriptive statistical methods will be used to summarize the data from this study, with statistical testing performed for the efficacy endpoints. All statistical testing will be two-sided and will be performed using a significance (alpha) level of 0.05. Unless stated otherwise, the term "descriptive statistics" refers to number of subjects (n), mean, median, standard deviation, minimum and maximum for continuous data, and frequencies and percentages for categorical data. Presentations of data will be summarized by treatment group and overall. The term "treatment group" refers to the following: Placebo or CX-8998. All available data for enrolled subjects will be listed in by subject listings. Unless otherwise noted, the data will be sorted first by treatment group, subject number, and then by date within each subject number.

All statistical analyses will be conducted with the SAS® System, version 9.4 or higher.

11.1 Statistical Analysis Plans

A SAP will be created and approved prior to the unblinding of the study data. This document will provide a more technical and detailed description of the proposed data analysis methods and procedures.

11.2 Study Hypothesis

The primary statistical hypothesis for the study is provided below.

- ∞ $H_{02}: \alpha_{\text{Placebo}} = \alpha_{\text{CX-8998}}$, i.e., there is no difference between treatment groups in the mean change from Baseline in TETRAS performance scale at end of treatment
- ∞ $H_{12}: \alpha_{\text{Placebo}} \neq \alpha_{\text{CX-8998}}$, i.e., there is a difference between treatment groups in mean change from Baseline in TETRAS performance scale at end of treatment

11.3 Determination of Sample Size

Up to 92 subjects will be randomized to one of two treatment groups: Placebo and CX-8998. Based on similarly designed studies, this sample size should be sufficient to provide preliminary safety and efficacy information on CX-8998 when administered according to this protocol.

A sample size of 43 subjects per group has at least 90% power to detect at least a 5.5 point difference between CX-8998 and placebo in change from Baseline to Day 28 in the TETRAS performance subscale when the standard deviation is 7.5 and alpha=0.05 (PASS 2008: Two sample t-test – Normal Non-Parametric Adjustment). Up to 92 subjects will be enrolled in order to ensure that 86 subjects are available for inclusion in the efficacy analyses.

11.4 Analysis Populations

The populations defined for analysis will include the intent-to-treat (ITT) population, safety population, and a pharmacokinetic population. Additional analysis populations may be defined to evaluate study results. Any additional analysis populations will be defined in the SAP.

- **Intent-To-Treat Population:** The ITT population will include all subjects who are randomized. The ITT population will be used for analyses of accountability, demographics, and efficacy. Subjects will be analyzed according to the treatment as randomized.
- **Safety Population:** The safety population will include all subjects who are randomized and receive at least one dose of randomized treatment. Subjects who receive treatment other than that intended will be analyzed according to the treatment received. The safety population will be the primary population for all analyses of safety data.
- **PK Population:** The PK population will consist of all subjects for whom PK samples were obtained, received study treatment, and for whom sufficient plasma concentrations are available.

Individual data for all enrolled subjects will be presented in data listings, sorted by treatment group and subject identifier.

11.5 Data Analysis

11.5.1 Efficacy Analyses

11.5.1.1 Primary Efficacy Analyses

The primary efficacy analysis of the TETRAS performance subscale (as scored by the central rater) will be conducted using an analysis of covariance (ANCOVA) model with fixed effects for treatment, concomitant anti-tremor medication use, site type, and Baseline value of the TETRAS performance subscale. The primary hypothesis to be tested will be if the mean change from Baseline in TETRAS performance scale

indicates that the CX-8998 arm is different from placebo. All testing will be performed using the LSMeans from the ANCOVA model and a two-sided test at the alpha=0.05 level of significance. If the data indicate a departure from the normal distribution, a corresponding rank test will be performed.

11.5.1.2 Secondary and Exploratory Efficacy Analyses

The proportion of subjects experiencing at least a 5.5 point decrease in the TETRAS performance scale will be summarized by treatment group. Differences between the treatment groups will be assessed with Cochran-Mantel-Haenszel General Association test stratified by concomitant anti-tremor medication use and site type.

The change from Baseline on the TETRAS Activity of Daily Living subscale and Total TETRAS score, change from Baseline to Day 28 in accelerometry score as measured by Kinesia ONE, change from Baseline in the ESS, change from Baseline on the QUEST scale, and the PGIC, the CGI-I, and GAS will be analyzed using the same type of ANCOVA model as described for the primary endpoint, with baseline values included only as applicable. All secondary and exploratory analyses will be conducted using two-sided tests at the alpha=0.05 level of significance. Analysis of findings from the neurophysiology sub-study will be presented in a separate study report.

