8.3.2 Clinical Global Impression

The Clinical Global Impressions Scale (CGI) was developed for use in NIMH-sponsored clinical trials to provide a brief, stand-alone assessment of the clinician's view of a patient's global functioning before and after initiating a study medication (Guy, 1976.) The CGI is a summary measure that takes into account all available information, including knowledge of the patient's history, psychosocial circumstances, symptoms, behavior, and the impact of the symptoms on the patient's ability to function.

The CGI has two forms—the CGI-Severity, which rates illness severity at baseline, and the CGI-Improvement, which rates change from baseline.

CGI-Severity (CGI-S). The CGI-Severity (CGI-S) consists of a single 7-point rating score of illness severity that is based on how ill the subject is relative to other subjects with whom the clinician has had experience. Raters select one response based on the following question: "Considering your total clinical experience with this particular population, how ill is the patient at this time?" Scores are: 1=normal, not at all ill; 2=borderline ill; 3=mildly ill; 4=moderately ill; 5=markedly ill; 6=severely ill; 7=among the most extremely ill patients.

CGI-Improvement (CGI-I). The CGI-I consists of a single 7-point rating of total improvement or change from baseline CGI-S, regardless of whether or not the change is due entirely to drug treatment. Raters select one response based on the following question, "Compared to your subject's condition at the beginning of treatment, how much has your subject changed?" Scores are: 1 = Very much improved; 2 = Much improved; 3 = Minimally improved; 4 = No change; 5 = Minimally worse; 6 = Much worse; 7 = Very much worse.

The CGI-S/CGI-I rater may have access to all clinical information related to subject severity and change, and does not need to be independent of other assessments. However, the rater who assesses the initial CGI-S should be the clinician who rates overall change via the CGI-I during the study. The rater will be a trained member of the site investigational team (clinician).

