(dosing days) orthostatic BP and pulse rate will be measured before dosing (recumbent and standing) and approximately 1-2 hours after dosing (recumbent and standing) as convenient between other required visit procedures. During any visit, blood pressure and pulse rate are to be assessed at any time subjects appear faint or complain of dizziness or other symptoms suggestive of hypotension. Respiratory rate and temperature will be measured in the recumbent position and need only be measured one time (with the first set of BP/pulse measurements). (Section 10.1.4.)

8. Clinical chemistry, hematology, urinalysis and coagulation panel. See Section 10.1.5 for complete details. Screening labs need not be repeated at Visit 1 (Day 1) if Day 1 is \leq 7 days from the screening visit. A positive drug screen will result in exclusion from the study unless it is explained by use of an allowed prescription medication (Section 10.1.6).
9. A triplicate 12-lead ECG will be performed at Screening and End of Study. At Visits 1, 2, 3 and 4 triplicate ECG will be performed predose and approximately 1-2 hours after the dose as convenient between other required visit procedures. All ECGs should be performed after at least 10 minutes of recumbency. (Section 10.1.8)
10. Women of childbearing potential only. A positive urine pregnancy test will be confirmed via serum testing. (Section 10.1.6)
11. Serum FSH only as needed to determine menopausal status in females < 62 years old with history of ≥ 12 months of amenorrhea without another cause.
12. Execution of the TETRAS Performance subscale will be video recorded for assessment by the central reader. Assessment by the site rater should be performed during the videotaping session. At Visit 1, the TETRAS Performance subscale should be performed prior to administration of study drug in the clinic. At Visits 3 and 4, the TETRAS Performance subscale should be performed during a window of 1 to 3 hours after administration of study drug in the clinic. (Section 8.1.1)
13. The Kinesia ONE device will be worn in the clinic after execution of the TETRAS Performance subscale assessment and, at Visit 1, prior to administration of study drug in the clinic. (Section 8.2.1)

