14. TETRAS ADL: A 12 item scale where each item is rated on a 0 to 4 scale, with 0 representing normal activity and 4 representing severe abnormality. The sum of the individual scores provides the overall score, ranging from 0 to 48. At Visit 1, the TETRAS ADL subscale should be performed after the TETRAS Performance subscale (performed during a window of 1 to 3 hours after administration of study drug in the clinic) and Kinesia ONE accelerometry and prior to administration of study drug in the clinic. At Visits 3 and 4, the TETRAS ADL should be performed after the TETRAS Performance subscale and Kinesia ONE accelerometry. (Section 8.1.2)
15. QUEST: a 30-item quality of life questionnaire (Section 8.3.1)
16. The Clinical Global Impression Severity (CGI-S) will be administered at Visit 1. The Global Clinical Impression Improvement (CGI-I) will be administered at Visits 3 and 4. (Section 8.3.2)
17. The Patient Global Impression of Change (PGIC) will be administered at Visits 3 and 4. (Section 8.3.3)
18. Subjects will identify 3 specific, personal goals at Visit 1. Progress towards the goals will be assessed via Goal Attainment Scaling (GAS) at Visit 4. (Section 8.3.4)
19. The Epworth Sleepiness Scale is intended to measure daytime sleepiness. (Section 10.1.10)
20. C-SSRS identifies behaviors that may be indicative of an individual's intent to commit suicide. Subjects answering "yes" to Suicidal Ideation item 4 or 5 on the C-SSRS during the study must be withdrawn from the study treatment. (Section 10.1.9)
21. The UM-PDHQ is a 20-item clinician-administered questionnaire that quantitatively and qualitatively assesses hallucinations. The UM-PDHQ will be completed for any subject who reports hallucinations. (Section 10.1.11)

22. Collection of samples will occur pre-dose on Visits 2, 3, and 4. Additionally, at Visit 4, a post-dose sample will be collected as close to 4 hours post-dose as possible, but within the window of 4-6 hours post-dose (i.e., a total of two PK samples are collected at Visit 4. [\(Section 9.1\)](#))
23. A sample for pharmacogenomic testing will be collected in all subjects except where prohibited by local regulation. [\(Section 9.3\)](#)
24. Concomitant medications will be recorded from the time of informed consent through the End of Study. See [Section 7.3](#) for a list of prohibited and restricted medications. At each visit, the study site staff will re-confirm the dose and schedule of other anti-ET drugs the subject is taking.

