8.3.4 Goal Attainment Scaling

Goal Attainment Scaling (GAS) is a tool that involves the development of a written set of goals between a physician and patient and is used for monitoring patient progress. GAS was developed in 1968 in response to the wide variety of evaluation models regarding mental illness and treatment (Kiresuk & Sherman, 1968). GAS has been employed in patients with physical disorders including spasticity (Ashford & Turner-Stokes, 2006) and multiple sclerosis (Kahn et al., 2008).

GAS frames the discussion in terms of individual patient-desired goals rather than universally applied health states. Goal-oriented care prompts patients to articulate which

health goals are most important to them. Patients and clinicians can then monitor progress in reaching them.

Subjects will identify 3 health goals at Baseline. Examples of goals are drinking from a cup, buttoning a shirt or ability to write. Goals may be either active or passive. All goals will be specifically tailored to the individual, with each subject required to rate each goal at baseline on the level of importance, based on a 3-point scale (1 = fairly important; 2 = very important; 3 = extremely important). For the investigator, the feasibility of attaining each goal must be considered before the goals are set and adjusted accordingly if needed. Once each goal is set, the investigator will be asked to rate the degree of difficulty in achieving each of the set goals, based on another 3-point scale (1 = probable; 2 = possible; 3 = doubtful.)

Progress towards each goal will be scored on a 5-point scale: -2 = Worse than Baseline (unfavorable outcome); -1 = No change from Baseline; 0 = Achieved the defined goal (expected outcome); +1 = Better than expected outcome; +2 = Best anticipated outcome.

Full details on Goal Attainment Scaling will be provided in the study Operations Manual.

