11.5.1.2 Secondary and Exploratory Efficacy Analyses

Analyses of the continuous secondary and exploratory endpoints will be conducted using the same type of ANCOVA model as described for the primary endpoint, with baseline values included only as applicable. All secondary and exploratory analyses will be conducted using two-sided tests at the alpha=0.05 level of significance. Analysis of findings from the neurophysiology substudy will be presented in a separate study report.

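### PGIC, CGI-I and GAS would, on the natural reading of the ANCOVA rule, be analysed without a baseline severity covariate, although suitable measures are taken at Visit 1 (minor; exploratory endpoints)

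*Protocol*

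**What the plan says.** The protocol file holds successive versions. The current one plans about 106 subjects.

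- **Reference model.** Section 11.5.1.1 specifies an ANCOVA with "fixed effects for treatment, concomitant anti-tremor medication use, site type, and Baseline value of the TETRAS performance subscale".
- **Current rule for other endpoints.** Section 11.5.1.2 states "Analyses of the continuous secondary and exploratory endpoints will be conducted using the same type of ANCOVA model as described for the primary endpoint", followed by "with baseline values included only as applicable". The synopsis, under secondary efficacy analyses, says the same.
- **Preceding version (up to 92 subjects).** Section 11.5.1.2 listed PGIC and CGI-I by name and closed the list with "GAS will be analyzed using the same type of ANCOVA model as described for the primary endpoint, with baseline values included only as applicable". That list is gone from the current text.
- **Status of the three scales.** Section 3.3.3 of the current version lists PGIC, CGI-I and GAS as exploratory, each as a measure of treatment success at the end of therapy.
- **What Visit 1 records.** The notes to the Schedule of Assessments say "The Clinical Global Impression Severity (CGI-S) will be administered at Visit 1" and "At Visit 1, the TETRAS Performance subscale should be performed prior to administration of study drug in the clinic". Section 8.3.2 ties the improvement scale to the severity scale: "The CGI-I consists of a single 7-point rating of total improvement or change from baseline CGI-S". For GAS, section 8.3.4 adds that "the investigator will be asked to rate the degree of difficulty in achieving each of the set goals".

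**The concern.** Leaving aside the substudy digital biomarkers, the other secondary and exploratory efficacy endpoints are changes from Baseline, so each has its own baseline value. The restriction in the clause therefore has an effect only for PGIC, CGI-I and GAS, which are scored only after treatment has begun. On that reading their models hold treatment, anti-tremor medication use and site type. Neither stratification factor measures severity.

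A global rating of change, or the attainment of a goal, may depend on how severe the tremor was at the start. If it does, a model without a severity term has a larger standard error than it needs, and a chance difference in severity between the arms is left unadjusted in the estimate. The trial already collects what is needed to avoid this, and CGI-S is the state against which CGI-I is defined.

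**Working it through.** **The plan's own figure.** The documents state no power or precision for PGIC, CGI-I or GAS. The only sample-size figure is for the primary endpoint: difference 5.5, SD 7.5, two-sided alpha 0.05, at least 90% power. A two-sample t-test needs 41 per group. Dividing by the rank-test efficiency 3/π gives 41 / 0.955 = 42.9, so 43, as the preceding version states. The current 53 per group also allows for dropouts and major deviations: 1 − 43/53 = 19% could be lost before falling to 43. Nothing in this point changes these numbers.

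**Inputs for the check.**
- n = 53 per arm, from section 11.3 of the current version, before losses.
- r, the correlation between baseline severity and the rating. It is not in the documents and is assumed to lie between 0.1 and 0.5.
- The rating is treated as continuous and linearly related to baseline severity.

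**Precision.** Adding one baseline covariate multiplies the standard error of the treatment effect by √(1 − r²). The equivalent sample size is n / (1 − r²). For an effect that the unadjusted comparison would detect with 80% power, the adjusted power is Φ(2.80 / √(1 − r²) − 1.96).

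| r | SE falls by | Equivalent n per arm | Power (80% unadjusted) |
|---|---|---|---|
| 0.1 | 0.5% | 53.5 | 80.4% |
| 0.2 | 2.0% | 55.2 | 81.6% |
| 0.3 | 4.6% | 58.2 | 83.6% |
| 0.4 | 8.3% | 63.1 | 86.4% |
| 0.5 | 13.4% | 70.7 | 89.9% |

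**Chance imbalance.** The standard error of the arm difference in a standardised baseline is √(2/53) = 0.194, so 95% of trials fall within 1.96 × 0.194 = 0.38 SD. An imbalance of that size moves the unadjusted estimate by r × 0.38 outcome SD: 0.04 at r = 0.1, 0.11 at r = 0.3 and 0.19 at r = 0.5.

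**Type I error.** In 20,000 simulated null trials with 53 per arm, the unadjusted test rejected in 0.049 (r = 0.3) and 0.048 (r = 0.5) of trials. The adjusted test rejected in 0.049 and 0.050. The unadjusted analysis is valid; it is only less precise.

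**The case against.** The strongest reply is that the current protocol fixes nothing here.

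- **The sentence naming the three scales is superseded.** The current rule covers continuous endpoints, and section 3.3.3 calls these three measures of treatment success. They might be analysed as success or failure, and the ANCOVA rule would then not reach them. This stands, and the point is limited to the case where ANCOVA is used.
- **The omission is inferred.** A model of the same type as the primary one could be taken to keep baseline TETRAS Performance, and section 11.1 leaves technical detail to the SAP. That reading is possible. It sits awkwardly with a clause that admits baseline values only where applicable, and a one-line clarification is worthwhile either way.
- **The unadjusted analysis is sound.** A reader might infer that imbalance in severity biases the result or makes it falsely significant. It does not. Randomisation makes the unadjusted estimator unbiased, its standard error already covers such imbalance, and type I error is held.
- **The gain may be small.** PGIC and CGI-I are already rated against the subject's own starting state, and GAS goals are tailored to the individual. A strong remaining correlation with severity is not shown in the documents.
- **GAS difficulty may already be used.** A reader might also infer that the investigator's difficulty rating belongs in the GAS model. Section 8.3.4 refers to the Operations Manual for full details, so the score may already use difficulty, and a covariate could partly duplicate it.

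What remains is that the clause, as it stands, directs the analyst away from covariates the trial already holds.

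**Conclusion.** The point holds as a minor, low-cost improvement. In the current text a natural reading leaves PGIC, CGI-I and GAS without a severity covariate whenever they are analysed by ANCOVA, while Visit 1 TETRAS Performance and CGI-S are available. The cost is lost precision and unadjusted chance imbalance on exploratory endpoints, and nothing more.

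The size rests wholly on an assumed correlation. The avoidable excess in standard error is slight at r = 0.1 to 0.3 (adjustment would lower it by 0.5% to 4.6%) and becomes noticeable only at 0.4 to 0.5 (8.3% to 13.4%). The documents do not support a claim that severity adjustment has been ruled out, that these results would be biased, or that any stated sample size or power is wrong.

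**What to change.** In section 11.5.1.2 and in the synopsis of the current version, replace the closing clause on baseline values with:

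> Each model includes the endpoint's own baseline; for PGIC, CGI-I and GAS, which have none, the model includes the Visit 1 TETRAS Performance score, or Visit 1 CGI-S for CGI-I.

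Do not add goal difficulty as a covariate for GAS unless the Operations Manual shows that the GAS score does not already use it. Settle the wording before unblinding, when the SAP must be approved in any case.

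The cost is one sentence in two places and one degree of freedom per model. No new data are needed and no stated sample size changes.

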11.5.2 Safety Analyses

Adverse Events will be mapped to a MedDRA-preferred term and system organ classification. Severity will be assessed by investigator. The occurrence of TEAEs will be summarized by treatment group using MedDRA-preferred terms, system organ classifications, and severity. All AEs will be listed for individual subjects showing both verbatim and preferred terms. Separate summaries of treatment-emergent SAEs and AEs related to study drug will be generated.

Descriptive summaries of vital signs and clinical laboratory results will be presented by treatment group and study visit. The number and percentage of subjects experiencing treatment-emergent laboratory abnormalities will be summarized by treatment group. Laboratory abnormality shifts from Baseline to post-Baseline assessments will be summarized by treatment group.

Concomitant medications will be mapped to a WHO preferred term and drug classification. The number and percent of subjects taking concomitant medications will be summarized using preferred terms and drug classifications.

Changes from Baseline in physical examinations, neurological examinations, and ECGs during study will be evaluated. Results from the C-SSRS will be listed by treatment.

